### **Serious Adverse Events of Special Interest**

Three serious adverse events are pre-specified as SAEs of special interest and were chosen for close monitoring by the sponsor medical monitor because of their clinical importance:

- 1) Wound dehiscence reported as an SAE
- 2) Wound hematoma reported as an SAE
- 3) Surgical site infection reported as an SAE

The detailed definitions for these surgical complications are in [Section 9.2.6](#). Details of the monitoring procedures are in [Section 9.3.4](#).

**Adverse Reaction**

An adverse reaction (AR) is any untoward and unintended response to a test drug that has been considered to have a causal relationship with the treatment.

**Suspected Unexpected Serious Adverse Reaction**

A suspected unexpected serious adverse reaction (SUSAR) is an adverse reaction that is serious and where the nature or severity of which is not consistent with information in the current Investigator's Brochure.

**Abnormal Laboratory Value as an AE**

An abnormal laboratory value (i.e. any clinical laboratory abnormality or change that suggests a disease and/or organ toxicity and is of a severity that requires active management [i.e. change of test drug dose, discontinuation of test drug, medical treatment, more frequent follow-up or diagnostic investigation]), will be regarded as an AE. If clinical sequelae have been associated with a laboratory abnormality the diagnosis or medical condition should be reported (e.g. renal failure, hematuria) to replace the laboratory abnormality (e.g. elevated creatinine, urine RBC increased).

**9.3.1.1 Classifications****Severity**

A blinded Investigator will evaluate the severity of each adverse event using the following definitions:

**Mild** – Transient symptoms, no interference with the patient's daily activities

**Moderate** – Marked symptoms, moderate interference with the patient's daily activities

**Severe** – Considerable interference with the patient's daily activities

An AE that has been assessed as severe should not be confused with an SAE. Severity is a category utilized for rating the intensity of an event; and both AEs and SAEs can be assessed as severe. An event should be described as 'serious' when it meets one of the pre-defined outcomes as described in [Section 9.3.1](#).

**Causality**

A blinded Investigator is obligated to assess the relationship between test drug and the occurrence of each AE/SAE. The Investigator will use clinical judgment to determine if there is a reasonable possibility that the pharmacological action of the test drug was responsible for the AE/SAE being reported. Alternative causes such as natural history of the underlying diseases, concomitant therapy, other risk factors, and the temporal relationship of the event to the test drug will be considered and investigated. The Investigator will also consult the Clinical Investigator's Brochure and/or Product Information, for marketed products, in the determination of his/her assessment.

After careful medical consideration, the Investigator will evaluate the relationship of each adverse event to test drug applying the following definitions:

**Probably Related** – Good reasons and sufficient documentation to assume a causal relationship

**Possibly related** – A causal relationship is conceivable

**Unlikely related** – The event is most likely related to etiology other than the test drug

**Not Related** – Good reasons and sufficient documentation to exclude a causal relationship.

There may be situations when an SAE has occurred and the Investigator has minimal information to include in the initial report. However, it is very important that the Investigator always make an assessment of causality for every event prior to transmission of the SAE Report Form to the Sponsor (or designee).

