## 7.3 Trial Test Drug

### 7.3.1 Test Drug Administration Instructions for SABER®-Bupivacaine and Saline Placebo

Using sterile technique, the test drug (either SABER®-Bupivacaine 5 mL [Part 1 and Part 2] or sterile normal saline 5 mL [Part 1 only]) will be drawn up into a 5 mL Norm-Ject® syringe using

a 16 G hypodermic needle, both of which will be supplied by the Sponsor. A small excess of test drug (approximately 5.5 mL) should be drawn up into the syringe to allow for dead space in the catheter used for administration. The 16 G needle will be removed and replaced with a plastic 14G x 1¼ inch CCI IV catheter (supplied by Sponsor) to aid in the administration of the test drug into all of the port incisions. Once the catheter has been attached to the syringe, the excess contents will be expelled through the catheter (along with any air) to bring the total quantity in the syringe to 5 mL. The test drug may be drawn up into the syringe up to one hour before dosing.

After removal of the trocars, desufflation of the abdomen, and closure of the fascial layer associated with the larger ports, the test drug will be administered sequentially into each of the port incisions. Each incision will be closed with a running subcuticular suture. Prior to tying the final knot, the plastic syringe-tip applicator (IV catheter) will be inserted into the wound and directed down to the level of the fascia. While pulling mildly upward on the free ends of the suture to create a virtual intra-incisional space, the prescribed quantity of test drug will be instilled into the incision via the syringe-tip applicator. The applicator should be gradually withdrawn while instilling test drug to ensure even distribution throughout the wound, and mild upward tension on the suture ends should be maintained to ensure the test drug remains entirely within the wound. The final knot will then be tied to complete closure of the incision. The patient number, drug vial number, date and time of drug administration (defined as the time of completion of administration), and the volume of test drug administered into each laparoscopic port will be recorded.

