### 9.3.4 Serious Adverse Events of Special Interest

Based on previous clinical experience, three serious adverse events are being pre-specified for close monitoring. The following pre-specified surgical wound complications, when reported as SAEs, are of special interest to DURECT CCI [REDACTED] (see [Section 9.2.6](#) for detailed definitions):

- 1) Wound dehiscence reported as an SAE
- 2) Wound hematoma reported as an SAE
- 3) Surgical site infection reported as an SAE

The sponsor medical monitor will carefully monitor the blinded safety data for any occurrence of these pre-specified SAEs. SAEs of special interest will be reported both to the Safety Assessment Committee (SAC), CCI [REDACTED] and to the FDA in accordance with safety reporting regulations. The expected incidence rate of the individual SAEs of special interest will be less than 1% based on the previous clinical experience with SABER-Bupivacaine and the published literature ([Richards et al, 2003](#); [Fahrner et al, 2014](#); [Keus et al, 2009](#); [Shea et al, 1996](#)). Non-serious instances of these surgical wound complications will be analyzed as AEs (as described in [Section 9.2.6](#) and [9.3.2](#))

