### **11.10 Statistical Analysis of Safety Endpoints**

#### **11.10.1 Safety Variables and Summaries**

Safety summaries will be based on the safety population. The safety population will include all subjects treated with SABER®-Bupivacaine 5 mL (660 mg bupivacaine base) or 0.9% sterile normal saline 5 mL (placebo) in Part 1; and all subjects treated with SABER®-Bupivacaine 5 mL or 15 mL of 0.5% bupivacaine HCl in Part 2. It will include summaries in the form of tables and patient listings by three treatment arms; SABER®-Bupivacaine 5 mL (660 mg bupivacaine base), 15 mL of 0.5% solution bupivacaine HCl (75 mg) or 0.9% sterile, normal saline 5 mL (placebo).

Safety variables include:

- Subject incidence rate of adverse events (both pre-specified patient-reported AEs solicited on LogPad through Study Day 4 [POD 3], as well as spontaneous AEs reported either by patient or investigator)

- Subject incidence rate of solicited AEs occurring in the first 6 hours after dosing of test drug.
- Time to the first occurrence of the solicited AEs
- Time to PACU discharge
- Change in standard 12-lead ECG at Screening, Visit 6 (Study Day 29), and Visit 7 (Study Day 60)
- Change in safety Laboratory Tests (serum chemistry, hematology, urinalysis) (Screening, Study Day 4, Study Day 29, Study Day 60)
- Change in vital Signs (heart rate, blood pressure, temperature, respiratory rate) (at each scheduled visit) and height, weight, BMI (Screening, Study Day 29, Study Day 60)
- CCI 

The subject incidence rate (number and percentage) of treatment emergent adverse events will be tabulated in each treatment group by MedDRA System Organ Class and Preferred Term. Summaries will also be presented by the severity of the adverse event and by relationship to test drug.

The individual rate of solicited patient-reported AEs (dizziness, somnolence, constipation, nausea, vomiting, pruritus, headache, dysgeusia, hypoesthesia, and paresthesia) will be derived. The risk ratio and 95% confidence interval (CI) for the individual AE rate will be presented with saline placebo and bupivacaine HCl as the control groups. For example, if the 95% CI for the risk ratio contains 1, the AE risk is considered comparable between the active and control groups.

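### The causality question in section 9.3.1.1 is limited to pharmacological action, which is narrower than the rating categories it feeds, so a wound event caused by the depot or vehicle could be rated unrelated

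*Combined protocol and SAP*

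**What the plan says.** Section 9.3.1.1 (Causality) first obliges a blinded investigator to "assess the relationship between test drug and the occurrence of each AE/SAE". It then states the question to be answered: whether to "determine if there is a reasonable possibility that the pharmacological action of the test drug was responsible for the AE/SAE being reported". The rating itself uses four categories: probably, possibly, unlikely and not related. Section 9.3.1 defines an adverse reaction as "any untoward and unintended response to a test drug that has been considered to have a causal relationship with the treatment", and a SUSAR is a serious adverse reaction not consistent with the Investigator's Brochure.

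The rating is used in section 11.10.1: "Summaries will also be presented by the severity of the adverse event and by relationship to test drug".

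The product and its safety focus are local. Under section 7.3.1, "the prescribed quantity of test drug will be instilled into the incision via the syringe-tip applicator" before the final knot is tied. The abbreviation list expands SABER as a sucrose acetate isobutyrate extended-release product, and sections 7.0 and 7.2 say that its viscosity and color un-blind operating-room staff. Section 9.3.4 states: "Based on previous clinical experience, three serious adverse events are being pre-specified for close monitoring". The three are wound dehiscence, wound hematoma and surgical site infection. Section 9.2.6 adds bruising, bleeding and drainage at each clinic visit.

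**The concern.** The question put to the investigator is narrower than the categories it feeds. A dehiscence, drainage or hematoma could plausibly arise from a viscous depot lying in the incision, from its vehicle or from the act of placing it there, without any pharmacological action of bupivacaine. No visible text says that such effects count as effects of the test drug. Two careful investigators could therefore rate the same wound event differently, depending on which sentence they follow.

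At stake are the related-AE counts in the clinical report and the step from AE to adverse reaction to SUSAR. The vehicle is given only to SABER-treated patients. If local wound events are more frequent with SABER, rating such events unrelated would shrink the absolute difference between arms in the related-AE table.

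**Working it through.** The plan gives no figure on this point, so there is nothing to reproduce. The check has three parts.

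**1. The texts side by side**

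| Place | Test applied | Limited to pharmacology? |
|---|---|---|
| 9.3.1.1, opening sentence | Relationship between test drug and event | No |
| 9.3.1.1, question to the investigator | Whether pharmacological action was responsible | Yes |
| 9.3.1.1, possibly related | "A causal relationship is conceivable" | No |
| 9.3.1.1, unlikely related | "The event is most likely related to etiology other than the test drug" | No |
| 9.3.1, adverse reaction | Causal relationship with the treatment | No |
| 11.9.1.2 and 11.9.1.3, Safety Assessment Committee (SAC) | SABER given, temporal relationship, no clear alternate cause | No |

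One sentence is out of line with the rest. A depot-caused dehiscence passes the possibly related definition and fails the question that leads to it.

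**2. What the rating reaches**

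- Uses it: the summaries by relationship (11.10.1), and adverse reaction and hence SUSAR status (9.3.1). On the latter, the sponsor also evaluates causality for all AEs (9.3.2).
- Does not use it: AE recording (9.3.2), SAE submission within 24 hours (9.3.3), surgical-site AE rates and risk ratios by treatment (11.10.1), and SAC stopping decisions (11.9.1.2, 11.9.1.3).

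**3. Illustration of size, on assumed rates**

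Inputs from the documents: 132 patients per arm in Part 2 (11.2), and about 90 in Part 1 randomized 1:1 (11.3), so about 45 given SABER. Safety tables use three treatment arms over both parts (11.10.1). This gives n = 132 + 45 = 177 for SABER and n = 132 for bupivacaine HCl.

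Assumptions, none from the documents: wound-AE rate p of 10% in control and 10%, 20% or 30% with SABER; share q rated related of 50% under broad wording and 10% under narrow wording, the same in both arms because raters are blinded.

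Expected related events = n × p × q. Related-AE risk difference = (p SABER − p control) × q. The ratio is p SABER / p control, in which q cancels.

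| p, SABER / control | Related at q = 50%, SABER / control | Related at q = 10%, SABER / control | Lost, SABER / control | Risk difference | Ratio |
|---|---|---|---|---|---|
| 10% / 10% | 8.85 / 6.6 | 1.77 / 1.32 | 7.08 / 5.28 | 0 → 0 points | 1.0 |
| 20% / 10% | 17.7 / 6.6 | 3.54 / 1.32 | 14.16 / 5.28 | 5 → 1 points | 2.0 |
| 30% / 10% | 26.55 / 6.6 | 5.31 / 1.32 | 21.24 / 5.28 | 10 → 2 points | 3.0 |

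With a milder fall, q from 50% to 25%, the difference goes from 5 to 2.5 points in the second row and from 10 to 5 in the third.

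SABER's share of the lost events is 7.08 / (7.08 + 5.28) = 57% in the first row, which reflects only 177 against 132 patients. It is 73% in the second row and 80% in the third.

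Worst case: raters recognise every excess SABER event as a vehicle or depot effect and rate it unrelated, with the other events still rated at q = 50%. The related rate is then 10% × 0.5 = 5% in both arms and the ratio is 1.0. The related events lost are 177 × (0.20 − 0.10) × 0.5 = 8.85 in the second row and 177 × (0.30 − 0.10) × 0.5 = 17.7 in the third.

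In every case the all-cause wound-AE rates and ratios are unchanged.

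**The case against.** The strongest reply is that the rating is made by applying the four definitions, not the sentence before them. A depot-caused dehiscence has the test drug as its etiology, so calling it unlikely or not related would breach those definitions. The alternative causes the investigator is told to weigh, such as underlying disease and concomitant therapy, are also external to the product. This stands against any claim that pharmacological action is the only test in the plan. It does not remove the conflict, because the question that leads into the definitions still says something narrower.

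A reader might also infer that related AEs would be lost mainly from the SABER arm. The documents do not support that. Raters are blinded, saline is instilled in the same way as SABER, and bupivacaine HCl is infiltrated into the incision margins, so placement effects can arise in every arm. A loss mainly from SABER needs an assumed excess of wound AEs with SABER. Lowering the ratio also needs blinded raters to recognise vehicle effects.

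The reach is limited as well. The main local safety comparison ignores relatedness, and the sponsor's own causality assessment is a second check on SUSAR classification. This stands, and it holds the point to a minor one.

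Finally, the Investigator's Brochure, which the investigator must consult, the Safety Monitoring Plan and the redacted part of 9.2.6 cannot be seen. Any of them might already say that vehicle and local effects count.

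**Conclusion.** The point holds as a minor wording defect. The stated causality question conflicts with its own opening sentence, its four categories and the adverse reaction definition, and it suits poorly a depot product whose events of special interest are wound events. It could understate related AEs in the by-relationship summaries and affect adverse reaction and SUSAR classification.

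The size cannot be established, because the documents give neither wound-AE rates nor the share rated related. If wound events are more frequent with SABER and raters discount them equally in both arms, the absolute related-AE difference shrinks and the ratio does not move. With equal wound-AE rates and equal discounting, neither the difference nor the ratio changes. It would go too far to conclude that the wording makes SABER look locally safer overall, since the all-cause surgical-site rates and risk ratios carry that comparison and are unaffected.

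**What to change.** In section 9.3.1.1, replace the reference to pharmacological action so that the question concerns the test drug (active substance, vehicle or other components, or its administration into the incision). Use identical wording for every arm and mirror it in the eCRF completion guidelines. This brings the question into line with the four categories and with the adverse reaction definition. Check the Investigator's Brochure and the unredacted section 9.2.6 for consistency at the same time.

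The cost is one phrase in the protocol and one in the guidelines, plus somewhat more events rated possibly related in all arms, because raters do not know which patients carry the depot. If events have already been rated under the present wording, the report should state when the wording changed.

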### 9.3.2 Adverse Event Reporting

All events that meet the definition of an AE that occur in the period from when the patient has signed the informed consent form (ICF) through trial completion (final visit), or early termination, must be recorded on the adverse event eCRF. All SAEs will be recorded on the appropriate eCRF and on the Serious Adverse Event Report Form from the time written informed consent has been obtained through trial completion (final visit), or early termination.

At each contact between the investigative site and the patient (visit or phone), after the patient has had an opportunity to spontaneously mention any problems, the Investigator should inquire about the occurrence of AEs. The following are examples of open-ended questions that may be used to obtain this information:

“How are you feeling?”

“Have you had any medical problems since your last visit/assessment?”

“Have you taken any new medicines, other than those given to you in this study, since your last visit/assessment?”

All AEs and SAEs will be documented in source records at each assessment time or when otherwise volunteered by the patient and recorded on the appropriate eCRF. Information to be collected includes the nature, date and time of onset, severity, duration, relationship to test drug, and outcome of the event. Even if the Investigator assesses the AE as not reasonably attributable to the test drug, its occurrence must be recorded in the source documents and reported on the eCRF along with the assessment of association.

The Investigator will treat the patient as medically required, and this may extend beyond the duration of the trial. The Investigator will record treatment and medications required to treat AEs on the appropriate eCRF(s). All AEs will be followed until resolution (no further changes in

the event are expected, i.e., the point at which a subject experiencing such an AE is appropriately treated and stabilized even though they may continue to experience lingering sequelae that may never resolve) unless the patient is lost to follow up.

DURECT will evaluate all AEs with respect to seriousness, causality and expectedness in accordance with [Directive 2001/20/EC](#) (3) and FDA Guidelines. The expectedness of an AE will be determined according to the current version of the Investigators Brochure.

### 9.3.3 Reporting of Serious Adverse Events

Regardless of causality, the investigator must complete and submit an SAE form to **CCI** Safety Surveillance within 24 hours of knowledge of the event for all serious adverse events.

**SAEs will be reported to:** **CCI** Safety Surveillance

**Fax:** **PPD** (toll free)

The Investigator must indicate the SAE's relationship to test drug and sign the SAE form. When additional relevant information (final diagnosis, outcome, results of specific investigations, etc.) becomes available, the investigator must record that follow-up information in the eCRF. Follow-up information should be recorded according to the process used for reporting the initial event as described above. The investigator will follow all reportable events (i.e., SAEs) until resolution. Resolution means no further changes in the event would be expected, i.e., the point at which a subject experiencing such an AE is appropriately treated and stabilized even though they may continue to experience lingering non-serious sequelae that may never resolve.

Safety Surveillance will follow all SAEs until resolution (no further changes in the event are expected, i.e., the point at which a subject experiencing such an AE is appropriately treated and stabilized even though they may continue to experience lingering sequelae that may never resolve). Safety Surveillance will report all SAEs to DURECT within 1 business day of receipt.

All serious adverse events will also be reported on the AE CRF and concomitant medications administered in association with the serious AE will be documented on the CM CRF.

If a serious adverse event occurs and comes to the attention of the Investigator after trial completion/termination within 60 days of test drug dosing or within 30 days of the last trial visit (whichever occurs later), it must be reported immediately to Safety Surveillance in the same manner as the serious adverse events occurring during the trial. Investigators are not obligated to actively seek AEs from former study participants.

The Investigator must report SAEs to the IRB/IEC (per the IRB/IEC guidelines/SOPs), including all SAEs that have occurred at the investigative site and all trial related SAEs that have resulted in an expedited safety report to a regulatory agency. Concurrently, the Investigator must send DURECT documentation of such IRB/IEC notification or if reporting is not required

immediately per IRB/IEC guidelines, then a copy of the local SOP stating the reporting guidelines should be supplied by the site to DURECT and the CRO.

DURECT complies with applicable regulatory requirement(s) related to the reporting of SUSARs to the competent authorities and the IRBs/IECs. In addition, DURECT will prepare annual safety reports covering all SUSARs that have occurred in clinical studies with the concerned test drug during the reporting period.

### 9.3.4 Serious Adverse Events of Special Interest

Based on previous clinical experience, three serious adverse events are being pre-specified for close monitoring. The following pre-specified surgical wound complications, when reported as SAEs, are of special interest to DURECT CCI [REDACTED] (see [Section 9.2.6](#) for detailed definitions):

- 1) Wound dehiscence reported as an SAE
- 2) Wound hematoma reported as an SAE
- 3) Surgical site infection reported as an SAE

The sponsor medical monitor will carefully monitor the blinded safety data for any occurrence of these pre-specified SAEs. SAEs of special interest will be reported both to the Safety Assessment Committee (SAC), CCI [REDACTED] and to the FDA in accordance with safety reporting regulations. The expected incidence rate of the individual SAEs of special interest will be less than 1% based on the previous clinical experience with SABER-Bupivacaine and the published literature ([Richards et al, 2003](#); [Fahrner et al, 2014](#); [Keus et al, 2009](#); [Shea et al, 1996](#)). Non-serious instances of these surgical wound complications will be analyzed as AEs (as described in [Section 9.2.6](#) and [9.3.2](#))

